13.1 Randomisation, stratification and blinding

Participants will be randomised to the wait list group (Group 1) or the initial intervention group (Group 2) using a one-to-one ratio, stratified by Country (Australia, UK), hospital (QCH, PA, TPC) and department [High risk (ED, ICU, isolation wards), lower risk (radiology, general wards, other)].

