13.2 Sample size calculations

There are no data in the literature on use of OM85 for the primary prevention of ARI, in relation to COV. However, 20% of Italy's HCW are infected with COV¹. If we assume 20% infection in Gp 1, then with 500 HCW in each group we will be able to detect a reduction in ARI in Gp 2 by 32.5% (to 13.5%) with 80% power ($\alpha=0.05$). Combined with 1000 UK-recruited HCW, we will be able to detect a 25% reduction (80% power, $\alpha=0.05$).

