13.2.1 Analysis sample

All participants randomised who receive at least one dose of study treatment will be included in the "intention-to-treat" group for statistical analyses.

Participants who complete the treatment period and take at least 80% of scheduled doses will be included in the "per protocol" group for statistical analyses.

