13.2.2 Statistical analyses

The *interim analysis*, undertaken at month 1 on both the "intention-to-treat" and "per protocol" groups, will examine the primary outcome: if the treatment difference is statistically significant in favour of OM85 the DSMB will consider immediately switching WLC participants to OM85.

Between-group differences in the primary outcome at 3 months will be assessed using log-binomial regression. Secondary outcomes measured to follow-up cessation will be assessed using mixed-effects models with group and stage (treatment/follow-up) (main effects and interaction) as fixed effects and HCW as random effect. Time-to-ARI analyses will use the log-rank test. Analyses will be undertaken on both the "intention-to-treat" and "per protocol" groups.

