13.3.1 Primary efficacy endpoint

The primary endpoint, defined in Section 7.2.1, will be analysed 3 months after enrollment using data collected prior to the WLC group commencing treatment, by comparing between-group differences in rates of ARI that necessitated workforce removal. The primary analysis will be conducted using log-binomial regression on both the "intention-to-treat" and "per protocol" groups.

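### The primary and interim analyses use two unranked analysis sets, and the per-protocol set gives no valid randomised comparison in months 0-3

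*Combined protocol and SAP*

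**What the plan says.** Section 13.3.1: "The primary analysis will be conducted using log-binomial regression on both the" intention-to-treat and per-protocol groups, using data from before the wait-list group starts OM85. Section 13.2.2 says the same of analyses in general and of the month-1 interim. The interim "will examine the primary outcome: if the treatment difference is statistically significant in favour of OM85", the DSMB will consider switching the wait-list group to OM85 at once.

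Section 13.2.1 defines the second set: "Participants who complete the treatment period and take at least 80% of scheduled doses will be included in the" per-protocol group. One rule covers both arms. The same section limits intention-to-treat to randomised participants who took at least one dose.

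Section 11.1 starts Group 1 dosing at Month 3. Section 13.2 sizes the trial on a single alpha of 0.05. No section names a lead set, gives a success rule for two sets, or adjusts for testing both.

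**The concern.** Two analyses share the label primary. If the all-randomised result were null and the per-protocol result favoured OM85, nothing in the plan would stop the second being reported as meeting the primary analysis.

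In a superiority trial a per-protocol contrast is not protected by randomisation. The wait-list design makes this worse: with a placebo, an adherence rule would filter both arms, whereas here, inside the primary window, it can filter only Group 2. The same two sets inform an interim look that could end the randomised comparison before Month 3.

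**Working it through.** **Inputs from the plan.** Section 13.2: "If we assume 20% infection in Gp 1, then with 500 HCW in each group", able to "detect a reduction in ARI in Gp 2 by 32.5% (to 13.5%) with 80% power"; and "Combined with 1000 UK-recruited HCW, we will be able to detect a 25% reduction". Section 13.1: allocation "using a one-to-one ratio, stratified by Country". Sidedness is not stated, so two-sided 0.05 is assumed (2.5% in favour of OM85). The documents give no adherence rate and no risk ratio between adherers and non-adherers, so those values below are assumptions.

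**The plan's own figure.** Pooled two-proportion test, 20% vs 13.5%, 500 per arm:
- Pooled risk 0.1675; SE under the null 0.02362; SE under the alternative 0.02353.
- Power = Φ[(0.065 − 1.96 × 0.02362)/0.02353] = Φ(0.795) = 78.7%, close to the stated 80%.
- 20% vs 15% at 1000 per arm gives 83.8%.

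The sample size therefore reproduces, as one test at one alpha.

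**Who is in the per-protocol set?** Setting 13.2.1 beside 11.1 and 13.3.1 leaves three readings:
1. Literal. Controls have neither started nor completed treatment by Month 3, so none qualifies and there is no comparison. At month 1 nobody in either arm has completed three months, so the interim set is empty.
2. Retrospective. Controls enter according to adherence in months 3-6, so they are selected on behaviour after the outcome window.
3. Dose rule waived for controls. Group 2 adherers are compared with all controls.

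None is a valid randomised comparison. The calculations below use reading 3, the most workable at 3 months.

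**Two tests, no selection.** Let a be the share of Group 2 kept in per protocol. The two statistics share all controls and the adherers, so under the null their correlation is 2/√[2(1/a + 1)]. For a = 0.8 this is 2/√4.5 = 0.943. The bivariate normal chance that at least one test is significant is:

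| a | Two-sided (nominal 5%) | In favour of OM85 (nominal 2.5%) |
|---|---|---|
| 0.9 | 6.1% | 3.0% |
| 0.8 | 6.6% | 3.3% |
| 0.7 | 7.0% | 3.5% |

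**Selection through baseline risk.** Assume no drug effect, overall risk 20%, and non-adherers at k times the adherers' risk. Adherer risk = 0.20/[a + (1 − a)k].
- a = 0.8, k = 1.5: 0.20/1.1 = 0.1818, a per-protocol risk ratio of 0.91. The chance of a false benefit from per protocol alone, at 800 vs 1000, is Φ[(0.0182 − 1.96 × 0.01868)/0.01860] = 16.1%; at 400 vs 500 it is 10.1%.
- a = 0.7-0.9, k = 1.25-2.0, 1000 per arm: 4.5% to 69%.
- a = 0.8, k = 0.8: 0.20/0.96 = 0.2083, a risk ratio of 1.04. False benefit falls to 0.8% at 1000 per arm.

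**Selection through the outcome.** Section 10.3 offers the early withdrawal visit to those who discontinue for reasons other than an ARI with workforce removal. That implies such an ARI can itself end participation, so Group 2 cases could fail the completion rule and leave per protocol. If 80% of Group 2 cases and 90% of non-cases are kept (assumed), the per-protocol risk is 0.16/(0.16 + 0.72) = 0.1818 against 0.20. Simulated chance (200,000 null trials) that either set shows a false benefit:

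| Cases kept / non-cases kept | 500 per arm | 1000 per arm |
|---|---|---|
| 80% / 85% | 5.5% | 7.4% |
| 80% / 90% | 10.4% | 16.8% |
| 70% / 85% | 20.0% | 35.6% |

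**The case against.** **A reader might infer that the plan compares OM85 adherers with unselected controls.** It does not say so. Section 13.2.1 has no exemption for controls, and that contrast appears only if one is supplied. This stands, but the other two readings are no better.

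**A reader might infer that the plan lets either set win.** It states no such rule; it is silent. Because the sets overlap, the cost of a second test without selection is also small, at most one percentage point in favour of OM85. Both parts stand, and the error rates above are therefore conditional on either set being allowed to carry the claim.

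**A reader might infer that per protocol must favour OM85.** The documents give no adherence data and nothing linking adherence to baseline risk. If healthier workers are the ones who stop capsules, the bias runs against OM85, as the ratio of 0.8 shows. The one pointer in the documents is 10.3, which points towards OM85. It is an implication only: 9.3.1 encourages those who stop the product to stay in follow-up, and 10.2 provides an unscheduled visit for an ARI rather than a withdrawal.

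**A reader might infer that the interim offers a working per-protocol route to switching controls.** Read literally, that set is empty at month 1, and the DSMB is asked to consider switching, not required to do it. What stands against the plan is that it calls for an interim analysis on a set its own definition leaves empty.

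**Conclusion.** The concern holds in this form: the primary and interim analyses run on two unranked sets, and in months 0-3 the per-protocol set gives either no control arm or a non-randomised contrast. That follows from the text and needs no assumption.

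The size does need assumptions. The second test alone is a minor matter. Selection is the larger risk, but its magnitude, and for baseline risk its direction, come from assumed inputs, so the 16% is an illustration and not an estimate for this trial. It is also a rate in favour of OM85, to be set against 2.5% and not beside the two-sided 6-7%.

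Ranking the intention-to-treat set first would not be enough, because its one-dose rule is met by no control inside the primary window and would drop controls who never start at Month 3. This is a should-fix: the defect is clear and the remedy simple, but the documents do not show that a biased claim would follow.

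**What to change.** State in 13.2.2 and 13.3.1 that the analysis of all randomised workers by allocated group is the sole primary analysis, and the only efficacy comparison used at the month-1 interim.

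In 13.2.1, 13.2.2 and 13.3.2, label per protocol, including its log-rank tests, as supportive, and state which controls enter it.

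The cost is wording. There is no new data collection, and on the plan's own assumptions power at 500 per arm stays at 78.7%.

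A complier-average estimate could be added as an optional supportive analysis, but only if dated adherence records exist. Section 10.2 and Appendix 1 schedule Group 2 drug collection only at Month 3, and no section specifies dated records of dose-taking. Its assumption of no effect in those taking under 80% of doses would need to be stated, since partial benefit there would make the estimate overstate the effect.

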13.3.2 Secondary efficacy endpoints and mechanistic endpoints

The secondary endpoints, defined in Section 7.2.2, and mechanistic evaluations, defined in Section 7.2.3, will be assessed using mixed-effects models with group and stage (treatment/follow-up) (main effects and interaction) as fixed effects and HCW as random effect. Time-to-ARI, including LRI, analyses will use the log-rank test.

These analyses will be undertaken, on both the “intention-to-treat” and “per protocol” groups, regardless of the outcome of the primary endpoint analysis.

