7.3 Mechanistic objectives

Mechanistic objectives of this study are to determine if OM85 modulates:

- Seroconversion to COV
- Host immune cell profile grouped who test respectively positive or negative to COV during an ARI, including LRI, and stratified by treatment (COV⁺/OM⁺, COV⁺/OM⁻, COV⁻/OM⁺, COV⁻/OM⁻).
- White blood cell transcriptomic profile by group (COV⁺/OM⁺, COV⁺/OM⁻, COV⁻/OM⁺, COV⁻/OM⁻).
- White blood cell cytokine production profile by group (COV⁺/OM⁺, COV⁺/OM⁻, COV⁻/OM⁺, COV⁻/OM⁻).

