8.2.3 Mechanistic endpoints

- Seroconversion to COV
- Host immune cell profile grouped who test respectively positive or negative to COV during an ARI, including LRI, and stratified by treatment (COV⁺/OM⁺, COV⁺/OM⁻, COV⁻/OM⁺, COV⁻/OM⁻).
- White blood cell transcriptomic profile by group (COV⁺/OM⁺, COV⁺/OM⁻, COV⁻/OM⁺, COV⁻/OM⁻).
- White blood cell cytokine production profile by group (COV⁺/OM⁺, COV⁺/OM⁻, COV⁻/OM⁺, COV⁻/OM⁻).

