10.2 Scheduled visits

This study consists of 5 visits (Group 1 - WLC) or 4 visits (Group 2 – initial treatment) over 6 or 9 months respectively (see Figure 1) Study procedures to be performed at each visit are detailed in the Schedule of Assessments and Procedures in Appendix 1.

Visits should be conducted within the specified visit windows where possible.

Figure 1: Study timeline and procedures. Nasal swab collection (blue arrow), blood collection (red arrow).

Group 1 (WLC)

Visit 1 – Screening and randomisation

The following assessments and procedures will be performed and recorded at this visit:

- Obtain written informed consent
- Evaluate inclusion and exclusion criteria
- Obtain demographic history
- Obtain medical history
- Vital signs
- Explain daily respiratory symptom data collection and assist with collection for Day 0

Once all screening procedures have been completed and eligibility confirmed, the participant will be registered with the Sponsor. Further information on the registration process is provided in the Study Reference Manual.

Visit 2: Treatment initiation 3 months post randomisation (±5 days)

- Update demographic & medical history
- Vital signs

- Nasal swab
- Collection of blood samples
- Dispense study medication and explain administration
- Adverse event assessment

Visit 3: Treatment cessation 6 months post randomisation (± 5 days)

- Vital signs
- Nasal swab
- Collection of blood samples
- Clarify any missing data (daily respiratory symptoms) with participant, if not previously addressed by email/SMS
- Adverse event assessment
- Collect used investigational product packaging and unused investigational product

Visit 4: Follow up cessation 9 months post randomisation (± 5 days)

- Vital signs
- Nasal swab
- Collection of blood samples
- Clarify any missing data (daily respiratory symptoms) with participant, if not previously addressed by email/SMS
- Adverse event assessment

Unscheduled Visit: at time of ARI necessitating workforce removal

- Vital signs
- Nasal swab
- Collection of blood samples
- Clarify any missing data (daily respiratory symptoms) with participant, if not previously addressed by email/SMS
- Adverse event assessment

Group 2 (Initial Treatment)

Visit 1 – Screening, randomisation, and treatment initiation

The following assessments and procedures will be performed and recorded at this visit:

- Obtain written informed consent
- Evaluate inclusion and exclusion criteria
- Obtain demographic history

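### For three of the four mechanistic endpoints, the model in section 13.3.2 has no COV term and no OM85 exposure term, so it cannot give the COV-by-OM85 comparison that the protocol names.

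*Combined protocol and SAP*

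**What the plan says.** Section 8.2.3 lists four mechanistic endpoints; section 7.3 and the synopsis list the same ones, and the synopsis limits them to Brisbane. Three are defined by the cells COV+/OM+, COV+/OM-, COV-/OM+ and COV-/OM-:

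- "Host immune cell profile grouped who test respectively positive or negative to COV during an ARI, including LRI, and stratified by treatment"
- "White blood cell transcriptomic profile by group", with the four cells in brackets
- "White blood cell cytokine production profile by group", with the four cells in brackets

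The other endpoint, "Seroconversion to COV", is an outcome in itself and has no cells. Only the immune cell endpoint ties COV status to an ARI. Section 7.3 gives the purpose: "Mechanistic objectives of this study are to determine if OM85 modulates" these measures.

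Section 13.3.2 gives the secondary endpoints and all the mechanistic ones a single method: "mechanistic evaluations, defined in Section 7.2.3, will be assessed using mixed-effects models". (Its cross-reference is to section 7.2.3; the definitions are in 8.2.3.) The terms are "mixed-effects models with group and stage (treatment/follow-up) (main effects and interaction) as fixed effects and HCW as random effect". Section 13.2.2 gives the same model for the secondary outcomes. Neither section has a COV term, an interaction with COV, or an analysis split by COV status.

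Section 13.1 uses group for the two randomised arms. Under section 8.1, Group 1 starts OM85 in Month 3 and Group 2 on day 0. Section 10.2 gives both groups an "Unscheduled Visit: at time of ARI necessitating workforce removal", with blood and swab taken, and does not limit it to any period of the study.

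**The concern.** The endpoint and its analysis do not match. The endpoint asks how the host response differs by COV status and OM85 status together. The model has no factor for COV, and its only treatment factor is the arm to which the worker was randomised. An analyst who follows section 13.3.2 would report group and stage coefficients that average over COV-positive and COV-negative samples. The question in section 7.3 would then go unanswered, or would be answered by a model chosen after the data were seen.

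There is also a point of interpretation. Having an ARI, and whether it is COV positive, are both settled after randomisation, and the primary objective is that OM85 should change who has an ARI. A contrast of OM+ with OM- among ARI cases therefore does not have the protection of randomisation, and the plan does not say so.

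**Working it through.** **Plan's own figure.** The documents give no power or cell size for the mechanistic analyses. Their nearest figure is in section 13.2: 80% power for 20% versus 13.5% with 500 per group, for the primary endpoint. With a two-sided 5% test and pooled variance:

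- pooled rate = (0.20 + 0.135)/2 = 0.1675
- SE under no difference = sqrt(2 × 0.1675 × 0.8325/500) = 0.0236
- SE under the alternative = sqrt((0.20 × 0.80 + 0.135 × 0.865)/500) = 0.0235
- z = (0.065 − 1.96 × 0.0236)/0.0235 ≈ 0.80, so power is 78.7%

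This agrees with the stated 80% to within 2 points. The point below does not depend on it.

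**Step 1: can the stated model give a COV contrast?** Let G be randomised group, S stage and C COV status, each coded 0/1. The stated fixed effects are

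E(Y) = b0 + b1·G + b2·S + b3·G·S.

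For a COV-positive and a COV-negative sample with the same G and S, the difference in fitted mean is 0, because C does not appear. A numerical check over the 2 × 2 × 2 = 8 combinations gives:

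- rank of the stated design: 4
- C in its column space: no
- G × C in its column space: no
- fitted COV-positive minus COV-negative difference: exactly 0 in all four group-by-stage cells
- rank after adding C and its interactions with G and S: 8, so the contrasts become estimable if every cell has data

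The random effect for HCW does not change this. It has mean zero and is not a COV coefficient.

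**Step 2: is group the same as OM85 status?** From sections 8.1 and 10.2:

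| Months since randomisation | Group 1 | Group 2 |
|---|---|---|
| 0 to 3 | not yet started | on OM85 |
| 3 to 6 | on OM85 | off, after the course |
| 6 to 9 | off, after the course | no scheduled visits |

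(Section 10.2 puts Group 2's last visit at 6 months and Appendix 1 prints Day 120. That needs reconciling but does not affect this point.)

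Group matches exposure in months 0 to 3 only. Stage, with two levels, can be read in two ways:

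- By each arm's own course: Group 1's waiting period, its only unexposed time, has no level, and the treatment stage compares OM85 with OM85.
- By calendar, with the first three months as treatment: Group 1's follow-up level mixes its on-treatment and off-treatment months.

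Neither reading gives an OM+/OM- classification over the whole study.

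**Step 3: how large might the cells be?** This is an illustration only. Apply section 13.2's 20% and 13.5% to 500 per group in Brisbane over months 0 to 3, assuming that every case is sampled. That gives 0.20 × 500 = 100 unexposed and 0.135 × 500 = 67.5 exposed ARI cases. The documents do not give the COV-positive share of ARIs. If it is assumed to lie between 5% and 50%:

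- COV+/OM-: 100 × 0.05 = 5 to 100 × 0.50 = 50
- COV+/OM+: 67.5 × 0.05 = 3.4 to 67.5 × 0.50 = 33.8

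So a correctly specified model may still have thin COV-positive cells.

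**The case against.** The best defence turns on one word. Section 8.2.3 itself calls the four cells groups, so group in section 13.3.2 could mean those cells, and a four-level factor would give every contrast. This reading is strained. The same sentence in 13.3.2 covers the secondary efficacy endpoints, section 13.2.2 repeats the model for secondary outcomes, and section 13.1 uses group for the arms. If it was intended, the text must say so, and OM85 status at sampling would still need a definition.

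It is also fair to say that these are Brisbane-only mechanistic endpoints with no bearing on the primary analysis or the month 1 interim decision. That limits the weight of the point but does not remove it.

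A reader might infer four stronger things. The documents do not support them:

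- **That every mechanistic sample comes from an ARI case.** The ARI timing is written for the immune cell profile only, and section 10.1.6 takes blood at four time points for serology and immune profiling.
- **That the plan files treated Group 1 samples under OM-.** Section 8.2.3 stratifies by treatment and does not say by randomised arm. The fault is that the model has no term for exposure.
- **That selection into ARI causes a bias or false-positive rate of known size.** This would need the correlation between each marker and the prevented cases, which the documents do not give. A figure that pooled COV-positive and COV-negative cases would also match none of the named contrasts.
- **That a Day 90 comparison of all Brisbane participants should lead.** It asks whether OM85 shifts the general immune profile, which is a different question from the response with and without COV. It could require many more assays, and Group 1 has no Visit 1 blood for baseline adjustment.

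**Conclusion.** The point holds for the immune cell, transcriptome and cytokine endpoints. Under the natural reading of group as the randomised arm, the model in section 13.3.2 returns a COV difference of exactly zero in every group and stage, whatever the data or sample size, and so cannot give the comparison the protocol names. Its group and stage terms also fail to classify OM85 exposure, because Group 1 passes from unexposed to treated and its waiting period has no stage level.

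The conclusion is structural. It rests on the text of sections 8.1, 8.2.3, 13.1 and 13.3.2 and on no assumed rate or correlation; the cell sizes above are illustrative. The change should be made before the mechanistic data are analysed. It does not affect the primary endpoint.

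**What to change.** In section 13.3.2, correct the cross-reference and give the three endpoints their own model:

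- **Fixed effects:** COV status; OM85 exposure at the sample date (not yet started, on treatment, off treatment after the course); and their interaction. That is 1 + 1 + 2 + 2 = 6 parameters for 2 × 3 = 6 cells. HCW stays as random effect.
- **Link to the endpoint:** say whether off-treatment samples count as OM+, so that the four named cells follow as contrasts of this model.
- **Samples:** say for the transcriptome and cytokine endpoints whether only ARI samples enter, as for the immune cell profile.
- **Interpretation:** state that having an ARI and COV status arise after randomisation, so OM+ versus OM- contrasts among ARI cases are associations and not randomised comparisons.

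Optionally, add a supportive comparison of Group 2 with Group 1 on the scheduled Day 90 blood, in randomised Brisbane participants whose samples are assayed. Section 10.2 lists Group 1's blood collection before dispensing at that visit; the SAP should specify that the sample precedes the first dose. It should also note that Group 1 has no Visit 1 blood for baseline adjustment.

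The required part costs SAP wording only and needs no new visit or sample. The downsides are that results from cases are described more cautiously and that some cells may be sparse, more so when exposure is split three ways. The optional comparison adds assay cost in proportion to the samples run.
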